 - For patients undergoing systemic treatment (alone or in combination with targeted treatment): If on post-treatment follow-up imaging within 3-12 months, lymph nodes seen on CT or MRI decrease by more than 30% in short axis diameter and PSA declines by more than 50%.

- If PSA increases by more than 50% on systemic therapy, then a increase in the size of lesion by more than 20% will be considered a true positive lesion.
- In subjects with localized suspected lymph node(s) receiving targeted treatment without concomitant systemic treatment there are two ways to meet true positive disease:
- If the subject shows a decrease of PSA by greater than 50% after targeted treatment and the lymph node does not enlarge (change in size less than 20% or less than 3 mm increase in short axis diameter) [OR]
 - If on post-treatment follow-up imaging within 3-12 months, lymph nodes seen on CT or MRI decrease by more than 30% in short axis diameter (with a minimum of 3 mm in change in size)
- For untreated patients: If on follow-up imaging within 3-12 months, lymph nodes seen on CT or MRI increase by more than 20% in short axis diameter (with a minimum of 3 mm in change in size).
- (2) False positive:
- For patients undergoing systemic treatment (alone or in combination with targeted treatment): If on post-treatment follow-up imaging within 3-12 months, lymph nodes seen on CT or MRI increase by more than 20% in short axis diameter and PSA decreases by more than 50%.
- In subjects with localized suspected lymph node(s) receiving targeted treatment without concomitant systemic treatment there are two ways to meet false positive disease:
- If the subject does not demonstrate a decrease of PSA by greater than 50% after targeted treatment [OR]
 - If on post-treatment follow-up imaging within 3-12 months, lymph nodes seen on CT or MRI increase by more than 20% in short axis diameter (with a minimum of 3 mm in change in size)
- For untreated patients: If on follow-up imaging within 3-12 months, lymph nodes seen on CT or MRI decrease by more than 30% in short axis diameter (with a minimum of 3 mm in change in size).
- (3) If all regions in a patient/region do not meet criteria for either True positive or False positive disease, then the patient/region will be considered inevaluable for primary endpoint.
- ii) Visceral lesions (non-lymph node soft tissue or organ) will be assessed by change in size. ⁶⁸Ga-PSMA-11 positive visceral lesions will be considered:
- (1) True positive:

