- For patients undergoing systemic treatment (alone or in combination with targeted treatment): If on post-treatment follow-up imaging within 3-12

months, lesions seen on CT or MRI decrease by more than 30% in long axis diameter and PSA declines by more than 50%.

- If PSA increases by more than 50% on systemic therapy, then a increase in the size of lesion by more than 20% will be considered a true positive lesion.

- In subjects with localized suspected lesions(s) receiving targeted treatment without concomitant systemic treatment there are two ways to meet true positive disease:

- If the subject demonstrates a decrease of PSA by greater than 50% after targeted treatment [OR]
- If on post-treatment follow-up imaging within 3-12 months, lesions seen on CT or MRI decrease by more than 30% in long axis diameter (with a minimum of 3 mm in change in size)

- For untreated patients: If on follow-up imaging within 3-12 months, lesions seen on CT or MRI increase by more than 20% in long axis diameter (with a minimum of 3 mm in change in size).

(2) False positive:

- For patients undergoing systemic treatment (alone or in combination with targeted treatment): If on post-treatment follow-up imaging within 3-12 months, lesions seen on CT or MRI increase by more than 20% in long axis diameter and PSA decreases by more than 50%.

- In subjects with localized suspected lesions(s) receiving targeted treatment without concomitant systemic treatment there are two ways to meet false positive disease:

- If the subject does not demonstrate a decrease of PSA by greater than 50% after targeted treatment [OR]
- If on post-treatment follow-up imaging within 3-12 months, lesions seen on CT or MRI increase by more than 20% in long axis diameter (with a minimum of 3 mm in change in size)

- For untreated patients: If on follow-up imaging within 3-12 months, lesions seen on CT or MRI decrease by more than 30% in long axis diameter (with a minimum of 3 mm in change in size).

(3) If all regions in a patient/region do not meet criteria for either True positive or False positive disease, then the patient/region will be considered inevaluable for primary endpoint.

iii) ⁶⁸Ga-PSMA-11 positive bone lesions will be considered:

(1) True positive:

- If there was a corresponding positive sclerotic lesion on the CT portion of the ^{68}Ga -PSMA-11 PET or on a separate CT obtained ≤ 30 days before or after the PET/CT in the same location as the PSMA uptake.

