- If there is focal uptake seen in the same location as the PSMA uptake on the baseline bone scan performed within one month of ^{68}Ga -PSMA-11 PET.
- If there is a lesion noted in the same location as the PSMA uptake on the initial MRI performed within one month of ^{68}Ga -PSMA-11 PET.
- If within 12 months follow-up CT demonstrates development of sclerosis in the same location as the PSMA uptake.
- If within 12 months follow-up MRI demonstrates a new bone lesion in the same location as the PSMA uptake.
- If within 12 months follow-up bone scan demonstrates new focal uptake in the same location as the PSMA uptake.
- In subjects with localized suspected bone lesion(s) receiving targeted treatment without concomitant systemic treatment:
 - o If the subject demonstrates a decrease of PSA by greater than 50% after targeted treatment.

(2) False positive:

- In subjects with localized suspected bone lesion(s) receiving targeted treatment without concomitant systemic treatment:
 - o If the subject does not demonstrate a decrease of PSA by greater than 50% after targeted treatment with curative intent (ie non-palliative radiation).
- If ^{68}Ga -PSMA-11 positive bone lesions do not meet the criteria for true positive findings, and appropriate correlative and follow-up imaging was acquired.

(3) If bone lesions do not meet criteria for either true positive or false positive disease listed above, then the patient/region will be considered inevaluable for primary endpoint.

iv) ^{68}Ga -PSMA-11 positive prostate bed and prostate lesions will be considered:

(1) True positive:

- For patients undergoing systemic treatment (alone or in combination with targeted treatment): If on post-treatment follow-up imaging within 3-12 months, lesions seen on CT or MRI decrease by more than 30% in long axis diameter
- In subjects with localized suspected lesions(s) receiving targeted treatment without concomitant systemic treatment there are two ways to meet true positive disease:

- If the subject demonstrates a decrease of PSA by greater than 50% after targeted treatment [OR]
- If on post-treatment follow-up imaging within 3-12 months, lesions seen on CT or MRI decrease by more than 30% in long axis diameter (with a minimum of 3 mm in change in size)

- For untreated patients: If on follow-up imaging within 3-12 months, lesions seen on CT or MRI increase by more than 20% in long axis diameter (with a minimum of 3 mm in change in size).

(2) False positive:

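### After targeted-only treatment, a PSMA-positive node or visceral lesion that grows while PSA rises more than 50% is scored false positive; untreated or on systemic therapy it is true positive, so PPV is biased downward

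*Combined protocol and SAP*

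**What the plan says.** Section 8.3.2 b) defines the follow-up reference standard separately for men on systemic treatment (with or without targeted treatment), men given targeted treatment only, and untreated men.

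**Lymph nodes, b) i)**
- Untreated, true positive: short-axis growth above 20% and at least 3 mm, with no PSA condition.
- Systemic, true positive: once PSA has risen by more than 50%, an "increase in the size of lesion by more than 20% will be considered a true positive lesion".
- Targeted only, false positive: for men "receiving targeted treatment without concomitant systemic treatment there are two ways to meet false positive disease", the first route is "If the subject does not demonstrate a decrease of PSA by greater than 50% after targeted treatment [OR" and the second is that "lymph nodes seen on CT or MRI increase by more than 20% in short axis diameter (with a minimum of 3 mm". The second route has no PSA condition.
- Targeted only, true positive: either a PSA fall above 50% in a node that has not enlarged, or shrinkage above 30% (at least 3 mm).

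**Visceral lesions, b) ii).** The structure is the same, on the long axis. The targeted-only growth route to false positive is "lesions seen on CT or MRI increase by more than 20% in long axis diameter (with a minimum of 3 mm". One difference matters below: the true-positive route through a PSA fall does not require that the lesion has not enlarged.

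**Prostate bed and prostate, b) iv).** The untreated true-positive rule and the two targeted-only false-positive routes match the visceral ones. On systemic treatment the only true-positive route is that "lesions seen on CT or MRI decrease by more than 30% in long axis diameter". No bullet covers growth with a PSA rise.

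**Bone, b) iii).** There is no growth bullet, and the false-positive rule based on PSA non-response is limited to targeted treatment given with intent to cure.

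**The concern.** A lesion that enlarges while PSA climbs is what the plan elsewhere takes as evidence of cancer. In the targeted-only branch the same pattern is evidence that PET was wrong, and the plan does not say why. A metastasis that was correctly seen but not controlled by local treatment would be recorded as a PET error. The label would then partly measure whether treatment worked, and PPV would not mean the same thing in each branch. Such a man or lesion also leaves the true positives on which the primary sensitivity rests; section 8.2.1 plans for 75 of them.

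**Working it through.** **Step 1: one record through the rules.** Take an illustrative lesion growing from 8 to 12 mm (+4 mm, +50%) with PSA going from 2 to 4 ng/mL (+100%).

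| Lesion | Untreated | Systemic | Targeted only |
|---|---|---|---|
| Node | true positive | true positive | false positive |
| Visceral | true positive | true positive | false positive |
| Prostate bed | true positive | inevaluable | false positive |

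In the targeted-only column the record meets both false-positive routes (PSA has not fallen by more than 50%; growth) and neither true-positive route. With a PSA rise of only 30%, the systemic node and visceral entries become inevaluable and the other two columns do not change. The full three-way conflict therefore needs a PSA rise above 50%.

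**Step 2: effect on PPV in the targeted-only branch.** The plan states no figure to reproduce. Assumptions:
- True PPV is 87%. Section 8.2.1 gives 87% for biopsy in the first cohort and calls it specificity, but also reports no true negatives, so reading it as a PPV is an interpretation.
- f is the share of true lesions in targeted-only men that progress in this way. The documents give no value.

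Observed PPV = 0.87 × (1 − f):
- f = 5%: 0.87 × 0.95 = 82.7%
- f = 10%: 0.87 × 0.90 = 78.3%
- f = 20%: 0.87 × 0.80 = 69.6%

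**Step 3: effect on per-patient sensitivity, all branches together.** False positives do not enter sensitivity. The loss arises because true positives leave while PET-negative men with biochemical disease stay as false negatives (8.3.2 d) i) (4)). Assumptions:
- 24% of men are PET-negative (8.2.1) and all count as false negatives, so 76% are PET-positive.
- The 24% also holds among cases with follow-up, and every PET-positive man is evaluable.
- PPV before relabelling is 87%.
- x is the share of all PET-positive men moved from true to false positive.

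Sensitivity = 0.76(0.87 − x) / [0.76(0.87 − x) + 0.24]:
- x = 0: 0.6612 / 0.9012 = 73.4%
- x = 5%: 0.6232 / 0.8632 = 72.2%
- x = 10%: 0.5852 / 0.8252 = 70.9%
- x = 15%: 0.5472 / 0.7872 = 69.5%

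A sensitivity of 70% needs true positives of 0.24 × 0.7 / 0.3 = 0.56, that is 0.56 / 0.76 = 73.7% of PET-positive men, so x = 87 − 73.7 = 13.3%. If PPV is instead taken as 100%, sensitivity starts at 76.0% and reaches 70% at x = 26.3%.

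**Step 4: linking the two scales.** If a share t of PET-positive men has targeted-only treatment, each with one evaluable region, then x = 0.87 × t × f. Even with t = 100%, f = 5% or 10% leaves sensitivity at 72.4% or 71.3%. With f = 20%, t must reach 0.133 / (0.87 × 0.20) = about 76% before 70% is reached. The documents give neither t nor f.

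**Step 5: per region.** A false-negative region requires positive pathology (8.3.2 d) ii) (4)), so the denominator holds few false negatives and regional sensitivity should move little. What is lost is the count of true-positive regions.

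**The case against.** The best defence is that this branch concerns localized suspected disease: if the only visible target is treated and PSA does not respond, the target may not have been the source of the PSA. That is a fair argument for the PSA bullet when the lesion has not grown. Such a record is inevaluable, not true positive, in the other branches, so it is not the contradiction described here. The argument does not explain why growth together with a rising PSA should refute cancer. The plan's other false-positive rules are more careful: the systemic growth rule also requires a PSA fall above 50%, and the bone rule requires curative intent.

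Safeguards exist. Under 8.3.2 d), a true positive in another region makes the patient true positive despite a false positive based on imaging or clinical follow-up. Pathology outranks follow-up, and investigators may depart from the criteria if they record it. These soften the effect. They do not help a man with one evaluable, unbiopsied region, and the last replaces a fixed rule with case-by-case judgement. The bias also runs against PET, so it cannot inflate the claim. That stands, but PPV would still be misstated.

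A reader might infer three stronger things that the documents do not support:
- That the prostate-bed rules contradict both other branches. The systemic branch has no rule for growth with a PSA rise.
- That any PSA rise produces the three-way conflict. The systemic rule needs more than 50%.
- That the primary criterion is put below 70%. Starting a calculation for this branch at exactly 70% would show that for any loss at all, but the criterion applies per reader to all cases with follow-up, not to one treatment branch.

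**Conclusion.** The contradiction stands for nodes and visceral lesions against both other branches, and for prostate-bed lesions against untreated men only. Its direct consequence is a downward bias in PPV, a secondary endpoint, of about 4 to 17 percentage points within the targeted-only branch (87% to 82.7%, and to 69.6%). This rests on an assumed 87% true PPV and an assumed 5% to 20% progression rate. The effect on overall PPV is diluted by the share of men in that branch, which is unknown.

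The effect on per-patient sensitivity is indirect. It threatens the 70% criterion only if about 13% of PET-positive men are relabelled (about 26% if PPV is taken as 100%). The documents do not show that this will happen. The point should be corrected, but it does not by itself undermine the primary analysis.

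**What to change.** Reconcile the targeted-only bullets in 8.3.2 b) i), ii) and iv) with the other branches before the central reads.

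1. Score growth above 20% (at least 3 mm) with a PSA rise above 50% as true positive, taking precedence over both false-positive bullets. For nodes and visceral lesions this follows the systemic rule. For the prostate bed it is an extension, supported only by the untreated rule.
2. Limit the growth false-positive bullet to growth with a PSA fall above 50%. For visceral and prostate-bed lesions, add to the PSA-fall true-positive bullet the no-enlargement condition that the node rule already has. Otherwise growth with a PSA fall above 50% meets both labels.
3. Score growth with a PSA change between these limits as inevaluable, and say that this overrides the PSA-only false-positive bullet. Without that sentence the record stays false positive.

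These steps settle the growth records. Shrinkage above 30% (at least 3 mm) without a PSA fall above 50% also meets both a true-positive and a false-positive route in all three lesion types, so the same revision should say which prevails.

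The cost is wording; the rules already use PSA and lesion size. The downside is that a benign lesion growing while PSA rises from disease elsewhere would be scored true positive. The plan already accepts that risk in its untreated branch and in its systemic node and visceral rules. Some records will also become inevaluable.

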Of our first cohort of patients, 19% of patients underwent biopsy after a positive PSMA PET imaging. Based on biopsy results there was 100% sensitivity and 87% specificity. There were no True Negatives or False Negatives on biopsy. Imaging follow-up is not complete for our first study so we cannot estimate the percent of patients that will have imaging follow-up, but it appears that roughly 15 to 20% of patients will have imaging follow-up. Consistent with our second protocol, we anticipated that the sensitivity for the four regions and for all regions combined using conventional imaging ranges from 30-60%. An overall sensitivity for ^{68}Ga -PSMA-11 PET of at most 50% will be considered as unacceptably low. Hence, the null hypothesis that the sensitivity is at most 50% will be tested against the alternative hypothesis that the sensitivity is greater than 50%. It is hypothesized that ^{68}Ga -PSMA-11 PET imaging on the per-region and per-patient basis will substantially increase the sensitivity for the four regions to at least 70%. A sample size of 75 true positives is required for rejecting the null hypothesis that the sensitivity is at most 50% with 90% power at the one-sided 0.01 ($=0.05/5$ – a Bonferroni adjustment for evaluating the sensitivity for the four regions and for all regions combined) significance level, assuming an average regions specific prevalence of 20%. Although 19% of patients underwent biopsy and 15% of patients have imaging follow-up, we anticipate that the biopsy rate will fall in this study as referring clinicians become more comfortable with the imaging results. Therefore, we will combine imaging and biopsy follow-up in the primary aim, and will require 375 with both imaging and/or biopsy follow-up in order to power the analysis at a per region level. Assuming a prevalence rate of 20% for disease in each individual region, a total sample size of 1,500 patients is required. In summary, the proposed target accrual of 1,500 patients (375 with biopsies or imaging follow-up) will provide adequate power for detecting the anticipated improvement in the sensitivity for both the per-patient and per-region based ^{68}Ga -PSMA-11 PET imaging. However, a sample size of 107 patients with biopsies/follow-up in total is sufficient for detecting the anticipated improvement in sensitivity when evaluating per-patient based sensitivity.

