 - For patients undergoing needle biopsy: Images of the procedure will be reviewed to determine if the correct node was biopsied.
 1. If the correct node was biopsied, then a negative biopsy will be considered a False Positive.
 2. If the incorrect node was biopsied, then follow-up imaging as described above will be performed.
- (b) Bone lesions: Given the high rate of false negative biopsies for osseous metastases in patients with prostate cancer, patients with negative bone biopsies of PSMA PET positive lesions will be further evaluated:
- If pathology demonstrates an alternative diagnoses that is known to be PSMA positive (eg Renal Cell Carcinoma metastases, Paget's disease), then this will be considered a False Positive.
 - If pathology is indeterminate, then follow-up imaging as described above will be performed.
- (3) Although not routinely performed during standard practice, immunohistochemical staining for PSMA of tumor specimens (primary and lymph node metastases) may be performed, although not required.
- d) Definitions of True Positive, False Positive, True Negative, and False Negative patients and regions: Pathology will be considered superior to imaging and clinical follow-up when available as described below. Patient and region level classification will be performed for each blinded reader, and be reported separately. The following criteria serve as a guide for interpretation. However not all findings on a lesions, region and patient level can be detailed here and investigators may deviate from these criteria in individual patients. These will be recorded for each interpretation that is not described in this protocol for the definition of a region or patient.
- i) Patient level evaluation:
- (1) True positive patient: A single region in a patient contains a true positive node either by pathology or imaging/clinical follow-up.

- (a) For a patient to be considered a True Positive, only one region is required to have a true positive lesion as described above, unless one region is categorized as a false positive based on pathology. This means that a single pathology false positive region outweighs regions with imaging/clinical follow-up true positive disease.
 - (b) A patient will be considered a True Positive if one region contains a lesion that is True Positive, even if other regions are categorized as inevaluable or false positive based on imaging or clinical follow-up.

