- (2) True negative patient: in the absence of True Positive or False Positive lesions, a patient will be considered a True Negative if there is pathology that is negative for disease and corresponding lesion is negative by PSMA PET.
 - (3) False positive patient:
 - (a) Pathology confirms a false positive lesion that is read as positive on PSMA PET.
 - (b) In the absence of pathology: there are no true positive regions, and there is a region that is categorized as false positive based on imaging or clinical follow-up.
 - (4) False negative patient: in the absence of True Positive or False Positive lesions, a patient will be considered a False Negative if there is pathology that is positive for disease and corresponding lesion is negative by PSMA PET. Additionally, patients without evidence of disease on PSMA PET but with biochemical evidence of disease will be considered a False Negative.
- ii) Region level evaluation: Each patient will have four evaluable regions (Table 1: prostate bed, pelvis, extrapelvic soft tissue, and bone metastases). Each region will be categorized as true positive or false positive as described above. Regions without evidence of PSMA positive disease or deemed inevaluable will not be included in the analysis.
 - (1) True positive region:
 - (a) Pathology confirms a PSMA avid lesion as a true positive in the region.
 - (b) In the absence of pathology, clinical or imaging follow-up demonstrates a true positive lesion within the region independent of the presence of an inevaluable lesion or a false positive lesion
 - ie true positive disease will supersede a false positive lesion in the region based analysis if based on imaging/clinical follow-up
 - (2) True negative region: in the absence of True Positive or False Positive lesions within a region, the region will be considered a True Negative if there is pathology that is negative for disease in the region and corresponding lesion is negative by PSMA PET.
 - (3) False positive region:
 - (a) Pathology confirms a PSMA avid lesion as a false positive in the region

- (b) In the absence of pathology, there are no true positive lesions in the region, and there is a false positive lesion by clinical or imaging follow-up.
- (4) False negative region: in the absence of True Positive or False Positive lesions in a region, the region will be considered a False Negative if there is pathology that is positive for disease in the region and corresponding lesion is negative by PSMA PET.

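### After targeted treatment, failure of PSA to halve makes a node, visceral or prostate-bed lesion a false positive whatever the treatment intent; only the bone rule is limited to curative treatment

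*Combined protocol and SAP*

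**What the plan says.** The rules are in section 8.3.2, Reference Standard Definition, part b). For subjects with localized suspected lesions who receive targeted treatment without concomitant systemic treatment, the node rule states that "there are two ways to meet false positive disease". The first is "If the subject does not demonstrate a decrease of PSA by greater than 50% after targeted treatment [OR", where the bracketed word marks it as sufficient alone. The second is growth of more than 20% with at least 3 mm of change. The PSA bullet recurs in the same words for visceral lesions, ii) (2), and for prostate-bed and prostate lesions, iv) (2).

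The bone rule, iii) (2), uses the same PSA test but only "after targeted treatment with curative intent (ie non-palliative radiation"). Bone lesions have a second route to a false positive: those that "do not meet the criteria for true positive findings, and appropriate correlative and follow-up imaging was acquired".

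On the true-positive side, a node qualifies if it shows a "decrease by more than 30% in short axis diameter (with a minimum of 3 mm in change in size"), whatever the PSA does, or if PSA falls by more than 50% and the node does not enlarge. For visceral, prostate-bed and bone lesions the PSA fall needs no accompanying size condition.

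Part d) sets the precedence. Pathology outranks follow-up. A patient with one true-positive region is a true positive even if other regions are false positive on follow-up. Within a region, "true positive disease will supersede a false positive lesion in the region based analysis if based on imaging/clinical follow-up". Part d) also says that "investigators may deviate from these criteria in individual patients", with such cases recorded.

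**The concern.** PSA sums over all the disease in a patient. Its failure to halve says little about one treated lesion if the treatment was not meant to eradicate that lesion. The bone rule recognises this; the other three rules do not. The word *localized* cannot be what excludes palliative treatment from those three, because the bone rule uses it too and still adds the qualifier.

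The node rule is also uneven. A PSA fall confirms a node only together with a condition on the node itself, whereas the absence of a fall refutes it with no lesion condition. The plan has an inevaluable category for lesions that follow-up cannot settle, but this bullet bypasses it.

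PPV, a secondary endpoint, is exposed directly. Per-patient sensitivity, the primary endpoint, is exposed indirectly: a relabelled man leaves the true positives, while PET-negative men with biochemical disease stay in the denominator as false negatives under d) i) (4).

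**Working it through.** **1. The four rules side by side (8.3.2 b), targeted treatment without systemic treatment).**

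| Lesion type | PSA route to false positive | Curative intent required? | PSA route to true positive |
|---|---|---|---|
| Node, i) | no fall >50% | No | fall >50% and node not enlarged |
| Visceral, ii) | no fall >50% | No | fall >50% |
| Bone, iii) | no fall >50% | Yes | fall >50% |
| Prostate bed, iv) | no fall >50% | No | fall >50% |

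All four are confined to localized suspected lesions, a term the plan does not define. None requires that every PSMA-positive site was treated.

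**2. One case traced through.** Take a malignant node treated palliatively, with no systemic treatment and no pathology. PSA does not halve and the short axis is unchanged.
- Node true-positive routes: neither is met.
- Node false-positive routes: the PSA bullet is met, so the node is a false positive. Without that bullet neither size criterion is met, and i) (3) would make it inevaluable.
- Patient level: if no other region is true positive, d) i) (3) (b) makes him a false-positive patient.
- The same history in bone: the PSA bullet does not apply, and the imaging criteria decide.

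**3. Effect on PPV.** The documents give no frequencies, so all inputs are assumptions: true PPV of 90%; s, the share of evaluable lesions on this pathway; q, the share of malignant lesions on it that are relabelled, that is, PSA does not halve for this reason and the shrinkage criterion is missed. Other lesions are taken to have the same true PPV and correct labels. Relabelled lesions stay in the denominator, so PPV = 0.9 × (1 − s × q).

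| s | q = 10% | 20% | 30% | 50% |
|---|---|---|---|---|
| 10% | 89.1% | 88.2% | 87.3% | 85.5% |
| 25% | 87.8% | 85.5% | 83.3% | 78.8% |
| 100% (targeted-treated lesions only) | 81% | 72% | 63% | 45% |

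For example, 0.9 × (1 − 0.10 × 0.20) = 0.882 and 0.9 × (1 − 0.25 × 0.30) = 0.8325. The formula ignores the precedence rules in d), which would reduce the effect in the region- and patient-level PPV that the plan reports.

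**4. Effect on per-patient sensitivity.** First, the plan's own figures (section 8.2.1). For 50% against 70%, one-sided 0.01 and 90% power, n = (2.326 × √(0.5 × 0.5) + 1.282 × √(0.7 × 0.3))² / 0.20² = 76.6, or 77 against the stated 75. Also 75/0.20 = 375 and 75/0.70 = 107.1, as stated. None of these depends on the false-positive rule.

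Now take 107 men at 70% sensitivity: 75 true positives and 32 false negatives, 75/107 = 70.1%. If a share f of the true positives is relabelled, sensitivity = 75(1 − f) / (75(1 − f) + 32).

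| f | Sensitivity |
|---|---|
| 5% | 71.25/103.25 = 69.0% |
| 10% | 67.5/99.5 = 67.8% |
| 20% | 60/92 = 65.2% |
| 30% | 52.5/84.5 = 62.1% |

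This start sits almost on the 70% success criterion, so small shifts cross it. With true sensitivity S, the criterion is reached at f = 1 − (7/3)(1 − S)/S, which is 22% for S = 75% and 42% for S = 80%.

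**The case against.** The best defence is that other text limits the damage. Pathology overrides follow-up. A true-positive region rescues the patient, and a true-positive lesion rescues its region. A lesion that shrinks past the threshold also meets the true-positive definition. Recorded deviations are allowed. All of this stands and narrows the effect. It does not help a man whose only evaluable lesion is stable or shrinks by less than the threshold, and case-by-case discretion is a weak substitute for a prespecified rule.

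A reader might go further than the text allows in four ways.
- *That the rules plainly reach men with other disease left untreated, and that the bone rule guards against this.* The reach depends on how *localized* is read. The bone qualifier concerns intent only and does not require all sites to be treated.
- *That diseased men with several sites are generally moved to false positive.* This happens only when no region is confirmed true positive; several sites give more chances of confirmation.
- *That a palliatively treated bone lesion escapes a false-positive label.* It can still receive one through the imaging route, or be true positive on a CT, MRI or bone-scan correlate.
- *That a PSA fall alone confirms treated lesions in any region.* For nodes it does not, because the node must also not enlarge. The question remains open for visceral, prostate-bed and bone lesions.

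**Conclusion.** The inconsistency is certain from the text: three of the four lesion rules let failure of PSA to halve decide a false positive whatever the treatment intent, and one does not. Its direction follows. PPV is biased downward and, where no other region is confirmed, diseased men leave the true positives used for per-patient sensitivity.

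Its size is unknown. If true PPV is 90% and the pathway holds 10% to 25% of evaluable lesions, PPV would be 78.8% to 89.1% for q between 10% and 50%. The range from 81% down to 45% might be taken as the reported PPV, but it applies only within targeted-treated lesions and rests on an assumed q. The sensitivity figures likewise rest on an assumed share relabelled. The sample size is unaffected. The limb about untreated disease elsewhere is conditional on an undefined term.

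**What to change.** Reconcile the four rules on treatment intent:
- Carry the bone rule's qualifier into the PSA false-positive bullets for nodes, visceral lesions and prostate-bed lesions. Classify lesions outside it by the size criteria or, if these are not met, as inevaluable.
- Define *localized* for this purpose. State whether all PSMA-positive sites must have been treated, and which read defines those sites, because classification is made separately for each blinded reader.
- State whether the same conditions apply to the PSA true-positive route, including whether a PSA fall alone can confirm visceral, prostate-bed or bone lesions in more than one treated region.
- Report a sensitivity analysis that applies the conditions to both routes.

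This changes how lesions are classified, not how patients are treated. The cost is wording in three bullets, a definition, a statement on the true-positive route and one further analysis. Treatment intent and treated sites must be abstracted from the clinical follow-up already scheduled in Appendix 2. Some lesions will become inevaluable. If the conditions are applied only to the false-positive route, a PSA fall still counts as true positive while no fall becomes inevaluable. That pushes PPV upward, and the plan should say so.
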